10.1.1 Evaluation of relationship of ADA with TEAEs

ation

10.2 Extent of exposure

Study medication administration and extent of exposure to the IMP as captured in the Study Medication Administration eCRF and treatment percent compliance (see note below for derivation) will be summarized and listed using the SS. The kit number and batch number

corresponding to each infusion will also be included within a listing of study medication administration.

The following categories will be included:

- Number of infusions received by study participant
- The duration of infusion will be calculated as follows:
Duration of infusion (min) = Stop time of infusion – start time of infusion + 1
- The total duration of exposure will be calculated as follows:
Exposure (days) = (Date of last dose – Date of first dose) + 28
- Time at risk (days) = (Date of last dose – Date of first dose) + 60
- Compliance: Compliance (%) will be defined as (Total volume delivered (mL) / volume planned) x 100% by visit. The following categories will be also included in the summary: Compliance <80%, ≥80 to ≤120 and >120% by visit
- Percentage of missed doses vs. the complete number of infusions intended per the protocol (12 infusions)
- Percentage of infusions where the length of infusion was too short. The length of infusion at Baseline is planned for the first dose 120 min (number and percentage of participants with length of infusion too short will be defined as <90 minutes). For all the post Baseline visit it is planned to be 60 minutes (number and percentage of participants with length of infusion too short will be defined as <45 minutes)

When SL0043 initially began, the planned infusion volume was 150mL. This was later changed to 200mL. Sites adopted the change from 150mL to 200mL infusions between Oct 2020 and April 2021.

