4.4 End of study definition

A study participant is considered to have completed the study if she/he has completed the Week 48 Visit.

The end of the study is defined as the date of the final visit of the last study participant in the study.

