8.3.1 Time period and frequency for collecting AE and SAE information

All AEs and SAEs will be collected from the signing of the ICF until the follow-up visit at the time points specified in the Schedule of Activities (Section 1.3).

In order to ensure complete safety data collection, all AEs occurring during the study (ie, after the signing of the ICF), including any pretreatment and posttreatment periods required by the protocol, must be reported in the eCRF even if no study medication was taken but specific study procedures were conducted. This includes all AEs not present prior to the initial visit and all AEs that recurred or worsened after the initial visit.

All SAEs will be recorded and reported to the Sponsor or designee within 24 hours, as indicated in Section 10.3. The Investigator will submit any updated SAE data to the Sponsor within 24 hours of it being available.

The Investigator is specifically requested to collect and report to UCB (or its representative) any SAEs (even if the Investigator is certain that they are in no way associated with the study medication), up to from the end of the study for each participant, and to also inform participants of the need to inform the Investigator of any SAE within this period. Serious AEs that the

Investigator thinks may be associated with the study medication must be reported to UCB regardless of the time between the event and the end of the study.

The method of recording, evaluating, and assessing causality of AE and SAE and the procedures for completing and transmitting SAE reports are provided in Section 10.3.

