2.3 Study design and conduct

2.3.1 Study description

The study will be conducted to demonstrate efficacy, safety and tolerability of DZP in study participants with moderately to severely active SLE despite stable nonbiological SOC medications (standard SLE therapy) and a persistent active or frequently relapsing remitting disease course or risk factors for relapsing remitting disease course to support regulatory filing.

The study is a randomized, double-blind, placebo-controlled, parallel group, Phase 3 study in study participants 16 years of age and older with moderately to severely active SLE who are receiving stable SOC medication (ie, antimalarials, corticosteroids, and/or immunosuppressants) in line with local and international guidance at Screening Visit (V1).

The study consists of a 2-week Screening Period, 48-week Treatment Period, and 6-week Safety Follow-up (SFU) Period (if the participant completes the study but decides not to enter the open-label extension (OLE) study SL0046). Due to the required moderate to severe disease activity at Screening visit (V1) and limited allowed treatment possibilities during the Screening phase, a short Screening Period is planned, see [Figure 2-1](#) below. At the start of the study, eligible study participants will be randomized (2:1) to DZP 24mg/kg or to placebo administered by iv infusion Q4W. The initial dose will be administered as a 2-hour infusion while each subsequent dose will be administered as a 1-hour infusion. Study participants who complete the 48-week Treatment Period may be eligible to participate in an OLE study (SL0046). Study participants who withdraw early from the 48-week Treatment Period will be followed up for at least 10 weeks after their final dose of study medication. Study participants who complete the study but choose not to enter the OLE will be followed up for at least 10 weeks after their final dose of study medication (ie, 10 weeks after last infusion at Week 44 which includes a 6-week SFU period).

Figure 2-1: Schema

BICLA=BILAG 2004-based Composite Lupus Assessment; BILAG=British Isles Lupus Assessment Group Disease Activity Index; BL=Baseline; CS=corticosteroid; DZP=dapirolizumab; EOS=End of Study; EOT=End of Treatment; N=number of study participants planned; OLE=open-label extension; PBO=placebo; Q4W=every 4 weeks; Scr=Screening; SFU=Safety Follow-up; SOC=standard of care; V=Visit; W/wk=week

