3.2 Analysis time points

The timeframe encompasses the entire study duration, which extends from Screening to 10 weeks after the final dose, ie, 48 weeks of the Double-Blind Treatment Period and 6 weeks of the SFU Period.

The following study periods will be included in the analysis (see Section 3.3 for the definition of Relative day):

- Screening Period: up to 14 days (Day -14 through Day -1).
- Double-Blind Treatment Period: 48 weeks, starts with the randomization (1:2) of eligible participants to 1 of 2 treatment arms (SOC + placebo [PBO] or SOC + DZP 24mg/kg), stratified in accordance with the 3 stratification factors (see Section 4.1). Study medication will be administered by iv infusion every 4 weeks, starting on Day 1.
- Safety Follow-up Period (SFU):
 - Participants who withdraw from the study prematurely will be followed up for at least 10 weeks after the last infusion.
 - Participants who complete the 48-week Double-Blind Treatment Period, but do not enter the OLE study will continue into a 6-week SFU Period (10 weeks after last infusion at Week 44). During this period, study participants will not receive study medication, but will be able to receive SOC treatment, as indicated.

The time points for individual assessments are provided in the schedule of activities in Section 1.3, Table 1-2 in the SL0043 protocol.

Analyses conducted by visit will include each planned study visit at which the assessment was scheduled. Data for planned study visits will be based on the nominal time point and will not include any unplanned visits. Usually, efficacy data will not be obtained at unscheduled visits, with the exception of lab data used in the BILAG grading process and for SLEDAI-2K. Here, labs that are obtained prior to the visit or up to 2 weeks after the original visit could be used to replace missing lab data (see separate Central BILAG Grading and Adjudication Plan for details on the BILAG grading process).

All data collected, including assessments (planned or unplanned) will be reported in participant data listings. Data from participants withdrawing from the study early at end of treatment (EOT) visits will be mapped to the next scheduled visit per assessment for purpose of analyses and inclusion in summary tables but will be presented in terms of nominal visit in listings.

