9 PHARMACOKINETICS AND PHARMACODYNAMICS

9.1 Pharmacokinetics (PK)

The following PK endpoints will be evaluated using the PK-PPS:

Samples from SOC+PBO participants will not be analyzed, except for the Week 48 assessment which will be considered the baseline for the OLE study SL0046. This data will be included in tables and figures of study SL0046 but not in SL0043. Individual study participant [REDACTED]

will be displayed graphically in linear and log scales. Geometric means with 95% confidence interval per visit will also be displayed graphically in linear and log scales. These values will be summarized per visit using the statistics described for continuous variables and in addition the number of participants with quantifiable samples, the geometric mean and the geometric coefficient of variation (assuming log normally distributed data). Tables and figures will only include data from the SOC+DPZ arm. Additional concentration by ADA participant status will be also generated. A listing will include all the data.

[figure not shown]
The lower limit of quantification (LLOQ) for DZP concentration in plasma is 0.2 μ g/mL. For the summary statistics, if a sample is BLQ, it will be considered as half of the LLOQ.

Descriptive summary statistics will be calculated only if 2/3 of the values are above the LLOQ at a given visit. If this is not case, only median, minimum and maximum values will be presented.

[figure not shown]
If data merit, a population PK analysis and PK/PD/Efficacy analyses may be conducted for the clinical efficacy endpoints and PD variables of interest. All population PK and PK/PD/Efficacy analyses will be described in more detail in a separate Data Analysis Plan, and results will be reported in a separate report.

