- Imputations for missing start dates will be handled according to the 'Imputation of Partial Start Dates' rules in Section 4.3.5.
- Imputations for missing end dates will not be performed for classification as treatment emergent and for calculation of time to onset as this is not required.
- In the listings, where AE onset and end date are the same, AE duration will be presented as <1 day.
- For AEs with end date >onset date, the duration will be presented in days. For the calculation of duration for AEs with missing start dates, the dates will be imputed as described in Section 4.3.5.
- In case of uncoded AEs, these AEs should be designated as “UNCODED” at all MedDRA levels, and such AEs will be included in summary tables and participant listings based on this classification.
- All TEAEs will be flagged in the listings. In addition, all TEAEs will be summarized, but pre-treatment and post-treatment AEs will only be listed.
- The following summaries will be created:
 - (1) Incidence of treatment-emergent adverse events (TEAEs) by MedDRA system organ class, high level term, and preferred term
 - (2) Exposure adjusted incidence rate of TEAEs (incidence rate/event rate) to include the number of events, number and proportion of participants with the event (ie, incidence proportion), the exposure-adjusted incidence rate per 100 participant years with the associated 95% confidence interval, and the exposure adjusted event rate per 100 participant years.

For exposure adjusted incidence rate, the numerator will be the total number of participants experiencing the AE, each participant counted only once even if the participant has the event multiple times. The denominator will be in 100 participant-years. That is, the total summation of individual participant-years at risk up to the first occurrence of the TEAE for participants with that AE, and the total participant-years at risk for those participants not experiencing that AE, divided by 100. Incidence rates will be presented with a 95% confidence interval. Exact Poisson 95% CIs for incidence rates are calculated using the relationship between the Poisson and the Chi-square distribution (Ulm, 1990).

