For exposure adjusted event rate, the numerator will be the number of AEs including repeat occurrences in individual participants. The denominator will be in 100 participant-years. That is, the total summation of individual participant-years at risk (total sum of "time at risk (last dose – first dose + 60)" for all participants) divided by 100. No confidence interval will be computed.

- (3) Incidence of Serious TEAEs
- (4) Incidence of serious TEAEs by relationship
- (5) Incidences of TEAEs by intensity, maximum intensity and by relationship at any time during the study
- (6) Incidence of TEAE of special interest (AESI)

Defined as any TEAE that a regulatory authority has mandated be reported on an expedited basis, regardless of the seriousness, expectedness, or relatedness of the AE to the administration of a UCB product/compound. For DZP, the following events require immediate reporting (within 24 hours regardless of seriousness) to UCB:

Hy's Law:

- Potential Hy's Law, defined as ≥ 3 xULN ALT or AST with coexisting ≥ 2 xULN total bilirubin in the absence of ≥ 2 xULN ALP, with no alternative explanation for the biochemical abnormality (ie, without waiting for any additional etiologic investigations to have been concluded). Follow-up information should be reported if an alternative etiology is identified during investigation and monitoring of the participant.
- Malignancies: haematological malignant tumours (SMQ), haematological tumours of unspecified malignancy (SMQ), non-haematological malignant tumours (SMQ) and non-haematological tumours of unspecified malignancy (SMQ).

- (7) Incidence of TEAE of special monitoring (AESM) as determined by the investigator. These are events of interest defined by the sponsor to be reported on an expedited basis to the sponsor, regardless of seriousness, expectedness, or relatedness of the AE to the administration of DZP
- (8) Incidence of TEAEs leading to temporary study drug discontinuation
- (9) Incidence of TEAEs leading to permanent study drug discontinuation or withdrawal from the study
- (10) Incidence of TEAEs occurring during treatment period (defined as last infusion + 28 days)
- (11) Incidence of opportunistic infection TEAEs (based on narrow SMQ for opportunistic infection)
- (12) Incidence of thromboembolic TEAEs (based on the “Emolic and thrombotic events” SMQ) (Note: this incidence table will be presented by maximum intensity)

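### Time at risk for adverse-event rates runs to last dose + 60 days with no stop at open-label extension entry, death or last contact, so the denominator can include time SL0043 does not observe

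*SAP*

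**What the plan says.** SAP 10.2 defines "Time at risk (days) = (Date of last dose – Date of first dose) + 60". SAP 10.1 uses the same quantity, "time at risk (last dose – first dose + 60", summed over every participant and divided by 100, as the denominator of the exposure-adjusted event rate. For the exposure-adjusted incidence rate, SAP 10.1 counts "participant-years at risk up to the first occurrence of the TEAE for participants with that AE"; participants without the event contribute their full time at risk. The treatment-emergent window in SAP 10.1 also runs from first dose to 60 days after last dose.

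Follow-up is described differently. SAP 2.3.1 gives the 6-week safety follow-up (SFU) only "if the participant completes the study but decides not to enter the open-label extension (OLE) study SL0046". SAP 3.2 says the same of completers who finish treatment "but do not enter the OLE study will continue into a 6-week SFU Period (10 weeks after last infusion at Week 44"). Protocol 4.4 states: "A study participant is considered to have completed the study if she/he has completed the Week 48 Visit". For pharmacokinetics, SAP 9.1 refers to "the Week 48 assessment which will be considered the baseline for the OLE study SL0046". Protocol 8.3.1 says: "All AEs and SAEs will be collected from the signing of the ICF until the follow-up visit".

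**The concern.** The formula assumes that everyone is under SL0043 observation for 60 days after the last dose. That is planned for completers who decline the OLE and for early withdrawals, both followed for at least 10 weeks after the last infusion. It is not planned for completers who enter SL0046, who leave SL0043 at Week 48, about 28 days after the Week 44 dose. It also fails for anyone who dies or is lost within the 60 days.

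The SAP does not say what happens to events in days 29 to 60 for OLE entrants, and neither possible reading is satisfactory:

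- **SL0046 events are not counted.** The Protocol 8.3.1 collection period and SAP 3.2 point this way. The denominator then contains unobserved time, and absolute rates per 100 participant-years are too low in both arms.
- **SL0046 events are counted**, because the treatment-emergent window is not closed at the first SL0046 infusion. Open-label events and time are then credited to the randomized arms. If placebo participants start active drug in the extension, the rate ratio is pulled toward 1.

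Two programmers could follow the text and produce different tables. Elsewhere the plan does censor: the discontinuation Kaplan-Meier plot in SAP 5.1 stops at the Week 48 or final visit, and time to flare in Protocol 9.3.2.2 stops at the last assessment.

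**Working it through.** **Inputs.** 12 planned infusions (SAP 10.2), every 4 weeks with the last at Week 44; Week 48 is Day 336 and the end-of-study visit is Day 378 (Protocol 1.3); treatment-period visit windows of ±3 days (Protocol 1.3); 208 DZP and 104 placebo participants (Protocol 9.8). OLE uptake, dropout and true rate ratios are not in the documents and are assumed.

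**Schedule check.** The plan states no person-time figure, but its schedule reproduces. Infusions: 44/4 + 1 = 12. First to last dose: 11 × 28 = 308 days. The exposure formula in SAP 10.2 (last − first + 28) gives 336, exactly Week 48. Ten weeks after the last dose is 308 + 70 = 378, the scheduled SFU visit.

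**One 12-dose OLE entrant, SL0046 events not counted.**
- Credited: 308 + 60 = 368 days. Observed: 336. Excess: 32 days, 32/368 = 8.7%.
- Visit windows: dose on day 305 and Week 48 visit on day 339 gives 26/365 = 7.1%; dose on day 311 and visit on day 333 gives 38/371 = 10.2%.

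**Arm level, event rate.** With everyone taking 12 doses, non-entrants followed for the full 60 days, a constant event rate and uptake u, the relative fall is u × 32/368:

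| OLE uptake (assumed) | Fall in event rate |
|---|---|
| 50% | 4.3% |
| 70% | 6.1% |
| 90% | 7.8% |

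At 90% uptake:
- DZP: credited 208 × 368/365.25 = 209.6 participant-years, of which 208 × 0.9 × 32/365.25 = 16.4 are unobserved.
- Placebo: 8.2 of 104.8.
- A true 300 events per 100 participant-years would read 300 × (1 − 0.0783) = 276.5.

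**With early stopping.** If 10–30% stop early (mean last dose at day 154, fully followed, both assumed) and uptake is a share of completers, the fall is 3.5–4.1% at 50% uptake and 6.3–7.4% at 90%.

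**Death or lost contact.** These add to the effect and are not limited to 8.7% per person. Six doses with contact ending 28 days after the last: credited 140 + 60 = 200, excess 32, or 16.0%. Twelve doses with death on the last infusion day: 60/368 = 16.3%. If 15% stop after six doses and one third of those are lost at 28 days, credited time averages 0.85 × 368 + 0.15 × 200 = 342.8 days. The excess is 0.85 × u × 32 + 0.05 × 32, that is 15.2 days (4.4%) at u = 0.5 and 26.1 days (7.6%) at u = 0.9.

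**Incidence rate.** Time stops at the first event, so the effect shrinks for common events. With a constant hazard of −ln(1 − p)/336 per day and 90% uptake, the fall is 7.6% for an event with 5% incidence by Week 48, 5.6% for 50% and 3.3% for 80%.

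**Between-arm ratio.** No change at equal uptake. At 90% against 70%: 0.9217/0.9391 = 0.981, a shift of 1.9%.

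**If SL0046 events are counted.** Assume that placebo entrants start open-label DZP at Week 48 with immediate effect. At 90% uptake the open-label share of placebo time is f = 0.9 × 32/368 = 0.0783. The observed ratio is RR/(1 + f(RR − 1)): a true 1.50 reads 1.44, and 2.00 reads 1.85.

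**The case against.** - **Size and use.** Of the 31 adverse-event summaries listed in SAP 10.1, only the second explicitly uses participant-years. No test or decision depends on it, and the bias largely cancels between arms. This stands and limits the weight of the point. But Protocol 9.4.1 commits to absolute rates per 100 patient-years, and those are the figures affected.
- **Assumptions behind 4.3% and 7.8%.** They require all 12 doses on schedule. With a last dose at Week 40 the excess is 4/340 = 1.2%; with a last dose at Week 36 or earlier and attendance at Week 48 there is none. Conversely, a Week 44 dose delayed to day 322, which footnote x of Protocol 1.3 allows, gives 46/382 = 12.0%. So the figures are illustrations, not bounds.
- **Planned follow-up.** Participants who stop drug are encouraged to attend all visits, and early withdrawals are followed for at least 10 weeks. That covers the 60 days when they attend. It does not cover OLE entrants, deaths or participants lost to follow-up.
- **Protocol 9.2.2 sends all completers into the SFU.** It omits the OLE exception that Protocol 4.1 and SAP 2.3.1 and 3.2 state; the more specific text governs.
- **Sixty days is deliberate.** The protocol synopsis ties it to five half-lives, and the numerator and denominator windows match on paper. True, and the length is not disputed. The windows match in practice only if events are captured throughout.
- **Redaction.** Large parts of the SAP are blacked out, and a handover rule there cannot be excluded. But the operative definitions in 10.1 and 10.2 are readable and refer to no cap.
- **Serious events.** Protocol 8.3.1 asks for serious events for a further period after study end, whose length is missing from the text, so serious-event rates may be less affected.

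**Conclusion.** The point holds on the readable text. The stated rule credits a 12-dose OLE entrant with 368 days against 336 observed, an excess of 8.7%. If SL0046 events are not counted, OLE entry alone lowers the event rate by 4.3% at 50% uptake and 7.8% at 90%, given the assumed uptake, 12 doses on schedule, full follow-up of non-entrants and a constant event rate. If they are counted, the randomized arms absorb open-label time and events. Which applies is not stated. Incidence proportions are unaffected in the first case. The table restricted to last infusion + 28 days uses neither this denominator nor the days 29 to 60 window. The consequence is confined to descriptive safety rates, but the rule is wrong as written and should be corrected.

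**What to change.** In SAP 10.1 and 10.2, end both time at risk and the treatment-emergent window at the earliest of: last dose + 60 days; first SL0046 infusion (or the SL0043 end date for OLE entrants); death; and last contact or study termination. State that SL0046 events are not counted in SL0043. The 60-day length stays as it is.

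The cost is SAP wording and one derived date per participant, with no new data collection. If SL0046 events were not going to be counted, rates rise slightly. If they were, both events and time are removed, so the direction of change is not fixed.

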10.2.1 Calculation of planned and actual dose received

The total planned dose given at each visit will then be calculated to 1 decimal place as follows:

Planned dose (mg) = Body weight (kg) x Randomized Dose (mg/kg).

The actual dose (mg) received will be calculated to 1 decimal place, and is based on the infusion volume given (mL) and the actual concentration of DZP in the infusion bag (mg/mL):

Actual dose (mg) = Infusion volume given (mL) x Concentration DZP in infusion (mg/mL).

The concentration of DZP in the infusion IV bag (mg/mL) is based on the number of mL of reconstituted solution from vials of DZP that were included in the IV bag and the total volume of the IV bag. There were 100mg DZP per every 1 mL of reconstituted solution from the vials.

Concentration DZP in infusion (mg/mL) =
{ [Sum across all vials used (amount of reconstituted solution taken from the vial (mL)) x 100mg/mL (DZP in the reconstituted solution)] / Total volume of IV bag prepared (mL) }

Percent of planned dose administered (%) is based on the actual dose compared to the planned dose, thus representing both the volume of infusion given as well as the actual contents of the IV bag, and will be calculated to 1 decimal place for each visit.

